6.3.1 Study Schedule

Preoperative period – Study Consent

Within 4 hours of existing operating room – Patches placed by study staff

Daily postoperative visit – reminder to enter information to the supplied iPhone

Day of discharge – Removal of patches by study staff

6.3.2 Informed Consent

Informed consent will be obtained using the documents reviewed and approved by the Yale IRB of the participant or their legally authorized representative. The process will be managed with the patient by a non-clinician member of the study team to avoid undue influence or coercion. The patient will be able to review the electronic informed consent document in the place and time of their own choosing.

6.3.3 Screening

Patients will be treated according to standard of care. The study team will perform a daily review of postings by colorectal surgeons included on this proposal ([name], [name], [name], [name], and [name]). Eligibility criteria used to review these postings will be accessible in the patient's electronic medical record.

6.3.4 Enrollment

Patients will be recruited by a non-clinician member of the study team by telephone. This device study represents low-risk. Informed consent will be obtained preoperatively by telephone. Patients will verbally hear a scripted consent by a member of the study team and be asked for their assent. If they agree, they will be electronically emailed a unique single-use REDCap link to complete the e-consent which will include the scripted paragraph heard earlier as well as all necessary consent components.

6.3.5 On Study Visits

Electronic informed consent – Average read time 10 minutes. Patients will be consented in electronic form and have up to 3 weeks to review document if desired and consent.

Postoperative patch placement – 5 minutes

Daily visit – 5 minutes

Day of discharge patch removal – 5 minutes

6.3.6 End of Study and Follow-up

End of study will be discharge of the patient and removal of patches, or early withdrawal by patient or clinician request.

30-days after discharge each patient's electronic medical record will be reviewed for documentation of primary and secondary end points and entered into a REDCap database.

6.3.7 Removal of subjects

During the study, it is possible that study subjects may be withdrawn from the study. If a withdrawal is related to the study procedure causing an adverse event, a Study Termination Form will be completed for each subject withdrawal. Factors that may lead to a withdrawal from the study may include, but are not limited to the following:

Subject Withdrawal

At any time, a study subject may voluntarily withdraw from the study. This withdrawal will not affect their future medical treatment or benefits.

Physician Decision/Medical Decision

Should a physician decide that the requirements of the protocol are detrimental to the health and welfare of the study subject, the study subject may be withdrawn from this study. The reason for the decision will be documented in the case report form. If the subject is found to not be wearing the device in its proscribed fashion and the data cannot be interpreted in its intended form, a member of the study team will complete a Study Termination Form and review with the principal investigator upon withdrawal.

6.4 Statistical Method

6.4.1 Statistical Design

6.4.2 Sample Size Considerations

This study aims to enroll 200 subjects. In a similar study¹ where subjects were enrolled and monitored after pancreaticoduodenectomy surgery, it was observed that 75 subjects

¹ Dua, M.M., Navalgund, A., Axelrod, S., Axelrod, L., Worth, P.J., Norton, J.A., Poulsides, G.A., Triadafilopoulos, G. and Visser, B.C., 2018. Monitoring gastric myoelectric activity after

provided the required power to detect significant difference between early and late oral tolerance diet groups. The increase sample size shown here is to observe myoelectric differences between right colon, left colon, and rectum resections.

6.4.3 Planned Analysis

6.4.3.1 Primary Analyses

The primary endpoint is to determine if there is a correlation between the measured motor activity metrics of the various GI organs with measures of recovery, and to mathematically characterize the correlation in a manner that leads to predictive ability. The study is retrospective without intention to treat. Data analysis is performed by the staff of G-Tech Medical located in Mountain View, CA using proprietary software developed specifically for this purpose. Data is accessed on a secure cloud server to which it was uploaded by the mobile app connected to the patches.

Data analysis consists of extracting the myoelectric motor activity measured by the patches in ten-minute time segments and assigning them to an organ or organs. The motor activity at any one time (instantaneous) and the cumulative activity up to that point in time will be examined for correlation to parameters associated with recovery rate such as time to first flatus, time to first solid meal, time to discharge, etc. This will be done across all time points to find the earliest time that offers predictive value. The specific final analysis approach taken will depend on the findings of this pilot study.

In the study² with colonic myoelectric activity measurements after open abdominal surgery an inverse correlation was found between cumulative colon signal strength and time to first flatus which was approximately linear and was best characterized by the root mean square (RMS) deviation of the residuals from a linear fit, in units of hours. The optimal time for this analysis was found to be at 36 hours after surgery.

Similarly in the study¹ with patients undergoing pancreaticoduodenectomy procedure, a correlation was found between cumulative signal strength of the stomach and time to first full meal that was also inverse but not well represented by a linear or other fit. In this case the analysis involved assigning patients to one of two groups, early and late feeders. The stomach activity data were then tested for predictive value against these groups. Patients with stronger signals were more likely to be in the early feeding group and vice versa. A statistical analysis was performed using a receiver-operator characteristic approach that led

pancreaticoduodenectomy for diet “readiness”. American Journal of Physiology-Gastrointestinal and Liver Physiology, 315(5), pp.G743-G751.

² Navalgund, A., Axelrod, S., Axelrod, L., Singhal, S., Tran, K., Legha, P. and Triadafilopoulos, G., 2019. Colon myoelectric activity measured after open abdominal surgery with a noninvasive wireless patch system predicts time to first flatus. Journal of Gastrointestinal Surgery, 23(5), pp.982-989.

to specificity and sensitivity values as a function of time after surgery, which allowed determination of the optimal time, which was again at approximately 36 hours.

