6.4.3.4 Analysis of Subject Characteristics

Descriptive statistics will be reported for age, sex, race, indication for surgery, type of anatomic resection, ostomy present preoperatively, ostomy present postoperatively, duration of operation, operative approach (open, laparoscopic, robotic).

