6.4.4 Subsets and Covariates

See subject characteristics above 6.4.3.4.

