7.6 Data Quality Assurance

Data will be stored and collected into two centrally cloud-based locations. Myoelectric signal data and clinical markers of recovery will be fed into G-Tech's centrally managed, deidentified cloud server via the G-Tech Patch Monitor App. Eligibility criteria, clinical history, and 30-day recovery will be abstracted by a member of the study team, input into REDCap with a study tablet, and stored locally at the Yale REDCap instance.

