7.8 Access to Source

Myoelectric signal analysis and G-Tech App clinical marker information will be provided back to the PI courtesy of G-Tech. The PI will use the unique identifier to re-link these results to the demographic and clinical characteristic data collected locally and held within REDCap.

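### No planned analysis separates the signal–flatus correlation from differences between types of operation

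*Combined protocol and SAP*

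**What the plan says.** Section 6.4.3.1 takes activity in ten-minute segments assigned to organs. Instantaneous and cumulative activity "will be examined for correlation to parameters associated with recovery rate such as time to first flatus" and to other recovery markers. No stratum, covariate or model is named, and the final approach is left to depend on the findings. Section 6.4.3.2 extends the correlation to ileus, readmission and first bowel movement, again without covariates.

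The text of 6.4.4 is "See subject characteristics above 6.4.3.4". That section begins "Descriptive statistics will be reported for age, sex, race, indication for surgery, type of anatomic resection", and operative approach comes later in the same list. The listed use is descriptive only.

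Secondary objective 4.3 asks whether signal patterns differ among right, left and rectal resections. Section 6.4.2 gives this as the reason for the larger enrolment: "The increase sample size shown here is to observe myoelectric differences between right colon, left colon, and rectum resections". It is a comparison of signals between sites, not of the signal–flatus relation within a site.

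Three other places matter:

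- **Case mix and its effects.** Section 5.3.2 admits open and laparoscopic, colon and rectal resections. Section 2.2 lists operative complexity and extent of bowel handling among the factors that govern the pace of recovery. Section 6.1.2 lets patch position move with the incisions.
- **Forms.** Appendix 3 records the procedure in four categories: the three sites plus Enterectomy Only. Appendices 2 and 3, as shown, have no field for operative approach, duration or indication, although 6.4.3.4 promises all three.
- **Data flow.** The manufacturer's staff run the signal analysis (6.4.3.1). On the clinical side, 7.6 says "Eligibility criteria, clinical history, and 30-day recovery will be abstracted by a member of the study team, input into REDCap". Under 7.8 the investigator will then "re-link these results to the demographic and clinical characteristic data collected locally".

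**The concern.** Resection type and approach are fixed before any patch is applied. The documents make it plausible that each is linked to the measured signal (4.3, 6.4.2, 6.1.2) and to speed of recovery (2.2). A variable linked to both can produce or conceal a correlation between them.

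The direction matters, because the earlier colonic study described in 6.4.3.1 found an inverse link: a stronger signal went with earlier flatus. If sites with weaker signals also recover later, the two shifts are opposite. They then add to, or imitate, the inverse link. If sites with weaker signals recover sooner, the shifts run the same way and work against it.

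Hypothesis 4.1 could therefore appear confirmed by differences between operations that the surgeon already knows, or a real within-operation link could be missed. Either would weaken the stated aim of predictive ability, since the plan has no analysis showing whether the signal adds to knowledge of the operation.

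**Working it through.** **The plan's own figure.** Section 6.4.2 states "This study aims to enroll 200 subjects". The basis is an earlier study in which 75 subjects "provided the required power to detect significant difference between early and late oral tolerance diet groups". No alpha, power, target correlation or group split is given, so 200 cannot be re-derived. Taking 75 for each of three sites gives 75 × 3 = 225, not 200. The figure is used below as given.

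**Assumed, because the documents do not state it.** Two-sided 0.05; three equal groups; group means at -d, 0 and +d within-group SD for both signal and time to flatus; one test at one time point. The extreme groups therefore differ by 2d in both variables.

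**Formulas.** The between-group variance of each variable is 2d²/3. With within-site correlation ρ, the unadjusted correlation is

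r = (ρ ± 2d²/3) / (1 + 2d²/3),

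with minus for opposite shifts and plus for same-direction shifts. The chance of p<0.05 uses Fisher's z: atanh(r) × √197, compared with ±1.96.

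**Creating a correlation (ρ = 0, opposite shifts).**

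| d | 2d²/3 | r | chance of p<0.05 |
|---|---|---|---|
| 0.25 | 0.042 | -0.042/1.042 = -0.04 | 9% |
| 0.5 | 0.167 | -0.167/1.167 = -0.14 | 52% |
| 0.8 | 0.427 | -0.427/1.427 = -0.30 | 99% |

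Simulation with 6,000 trials per row gave 8.9%, 51.8% and 99.4%. The same test within resection type gave 4.6%, 5.4% and 4.4%.

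**Masking a correlation (ρ = -0.3, same-direction shifts).**

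| d | r | chance of p<0.05 |
|---|---|---|
| 0 | -0.30 | 99% |
| 0.25 | (-0.3 + 0.042)/1.042 = -0.25 | 94% |
| 0.5 | (-0.3 + 0.167)/1.167 = -0.11 | 36% |
| 0.75 | (-0.3 + 0.375)/1.375 = +0.05 | 12% |

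In simulation (3,000 trials each) the site-adjusted correlation kept about 99% power at d = 0.25, 0.5 and 0.75.

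**Unequal groups.** With shares of 40/40/20, ρ = 0 and opposite shifts, d = 0.25 and 0.5 give 8% and 41%.

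**Approach alone.** Assume 30% open surgery and a 1.0 SD shift in both variables, in opposite directions. The between-group variance is 0.3 × 0.7 = 0.21, so with ρ = 0, r = -0.21/1.21 = -0.17, and p<0.05 in 69% of trials.

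**Precision per site.** With 200/3 ≈ 67 patients, the correlation detectable with 80% power is tanh((1.96 + 0.84)/√64) ≈ 0.34. For all 200 it is tanh(2.80/√197) ≈ 0.20.

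**The case against.** Several points on the other side are fair.

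- **Pooling is not stated.** A reader might infer that the plan has decided to analyse all patients as one group. No section says so. Section 6.4.4 does designate resection type and approach as subsets or covariates, and 6.4.3.1 leaves the final method open. What stands is that no analysis using them is specified.
- **The data flow does not block adjustment.** A reader might infer from 7.6 and 7.8 that nobody analysing the signal can know the operation. Section 6.1.1 makes the measurements available to the investigators for correlation, 6.4.3.2 plans correlation with record-derived outcomes, and 7.8 creates a linked file at the site. Section 7.3 keeps only direct identifiers out of the data given to the manufacturer. This objection succeeds: the missing piece is a model statement, plus a form field for approach.
- **The protocol does not assert that signals differ by site.** Objective 4.3 poses it as a question. Section 6.4.2 comes closer, but the documents support no more than plausible.
- **Adjustment is not automatically the right primary estimate.** If an operation lowers colonic activity and thereby delays flatus, adjusting removes part of the link. For prediction in a feasibility study, the unadjusted relation has its own use. This stands, and it is why both estimates should be reported rather than one demoted.
- **The shift sizes are assumed.** This also stands. At d = 0.8 the extreme sites differ by 1.6 SD in both variables, in exactly reverse order, which is a strong assumption.

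**Conclusion.** The gap is real. The plan correlates signal with recovery and specifies no analysis that separates this from differences between operations, although its own text makes both confounding paths plausible.

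The size is conditional. Under the assumptions above, distortion is small at 0.25 SD per site step and substantial from about 0.5 SD: about 52% false positives with opposite shifts, or power down from about 99% to 36% with same-direction shifts. The documents give no between-site difference in signal or in time to flatus, so they do not support a claim that the study's correlation will be distorted, only that it could be and that the plan would not detect it.

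The roughly 5% error rate after adjustment applies to one test at one time. Section 6.4.3.1 searches all time points and several markers and states no significance rule, so adjustment alone would not give the plan that error rate. The change is worth making because resection type is already collected and adjusting for it costs very little.

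**What to change.** 1. In 6.4.3.1 and 6.4.4, prespecify the association of colon activity with time to first flatus, adjusted for or stratified by resection type as recorded in Appendix 3, and for operative approach.
2. Report it beside the unadjusted correlation. Base any claim that the signal adds information beyond type of surgery on the adjusted estimate.
3. State how the Enterectomy Only category is handled, since it lies outside the three sites in objective 4.3.
4. Add operative approach, duration and indication to Appendix 3. Section 5.3.2 names two approaches and 6.4.3.4 names three, so agree the levels of that field.
5. Run the adjusted analysis on the linked file that the site creates under 7.8. Alternatively, send coded resection type and approach by study number to the manufacturer's analysts, which 7.3 allows.

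**Cost.** SAP wording and three form fields. Three resection sites and three approaches use 2 + 2 = 4 degrees of freedom out of 200, or 5 if Enterectomy Only is kept as its own level. Per-site estimates will be imprecise (detectable r about 0.34 at 67 per site) and should be presented as such.

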2.1.2 Device Clinical Experience

This technology has been studied as part of several non-significant risk IRB approved studies in both adults and pediatric populations to evaluate the patterns of gastrointestinal myoelectrical signals following surgery.²⁰⁻²² The studies demonstrate that signals measured by the G-Tech Wireless patches correlate with clinical markers of postoperative recovery such as time to feeding and time to flatus following pancreaticoduodenectomy and general abdominal surgeries respectively. The study in patients undergoing pancreaticoduodenectomy procedures was conducted in collaboration with researchers at Stanford University.²⁰ The study demonstrated that measurement of gastric activity beginning immediately after pancreaticoduodenectomy with the G-Tech Wireless Patch System, based on the measured spectral peak near 3 cpm, could distinguish patients with shorter or longer times to diet readiness. The study demonstrated the potential utility of the G-Tech Patch System in providing objective data to identify patients who are progressing as well as, or better than expected, and those who are at risk for delayed gastric emptying. In another open, prospective study, researchers examined the use of the G-Tech Wireless Patch System in predicting time to first flatus by looking at colonic myoelectrical activity following general abdominal surgeries.²¹ Patients with early flatus had stronger early colonic activity than patients with late flatus. At 36 h post-surgery, a linear fit of time to flatus vs cumulative colonic myoelectrical activity predicted first flatus as much as 5 days (± 22 h) before occurrence.

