At present, there is no reliable measurement that can predict gastrointestinal recovery/diet readiness for patients in advance of these clinical markers that may allow for interventions or fast-track programs to facilitate timely recovery. Auscultation for return of bowel sounds, long part of the standard of care, is controversial in its usefulness to indicate recovery. Bowel sounds have shown to have poor correlation with flatus/defecation and have proved unsuccessful in guiding diet interventions.^{12,13}

Smooth muscle electrical activity on the other hand is directly related to gastrointestinal function and motility. Researchers have previously shown a 1:1 correlation between electrical and mechanical (contractile) events in the colon with internally placed electrode-strain gauge force transducers.¹⁴⁻¹⁶ Electrical activity in the colon has been reported across a wide range of frequencies ranging from 0 to 40 cycles per min (cpm)).¹⁷ Condon et. al have documented the progressive return of colonic electrical activity related to resolution of postoperative ileus and clinical recovery following surgery.^{18,19} These measurements have been performed using electrodes placed internally during surgery, a major impediment towards broader use of such technology.

3 Rationale/Significance

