3.2 Purpose of Study/Potential Impact

The purpose of the Phase 1 study is to determine if the myoelectrical measurements made by the G-Tech Wireless Patch System correlate with clinical markers of postoperative recovery such as passage of flatus/bowel movement, oral tolerance of diet and discharge readiness. Subsequently the data will be studied to establish which information in the signals is important in determining when to feed patients and possibly discharge them.

These pilot prospective, open clinical studies suggests that myoelectrical activity, measured on the abdominal surface with a noninvasive wireless patch system, carries predictive value in determining time to feeding and time to flatus following open abdominal surgery. Having such information in advance of clinical measures could facilitate timely interventions, be it early feeding or delaying feeding as dictated by the patient's unique recovery profile. The G-Tech Wireless Patch System would provide a unique insight into the process allowing for a tailored protocol that could improve patient satisfaction and optimize recovery. The system could also enable feedback on the impact to the overall gastrointestinal myoelectrical activity of medications, particularly opioids, used for pain management that are known to inhibit gastrointestinal function by disrupting the normal recovery patterns of colonic motility.²³⁻²⁵ While it remains to be seen, in addition to predicting time to flatus/bowel movement early on, the ability to continue monitoring the patient may allow one to predict onset of secondary complications, such as wound infections or anastomotic leaks, that are associated with ileus. Although not part of this protocol, given the wireless noninvasive nature of the system the patients could be discharged home with the patches, whereby they would serve as a remote monitoring tool. This could be particularly useful in cases where the patients may have been discharged early and may be at a high risk for readmission. The system would then send updates/alerts to the care team for management and potentially avoid preventable readmissions.

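### Predictive claims for first flatus are not limited to patients who are still flatus-free at the time point in question

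*Combined protocol and SAP*

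**What the plan says.** Section 6.4.3.1 makes prediction part of the primary endpoint: the aim is to find a correlation and "to mathematically characterize the correlation in a manner that leads to predictive ability". Activity is extracted in ten-minute segments. Both the instantaneous value and "the cumulative activity up to that point in time will be examined for correlation to parameters associated with recovery rate", with time to first flatus the first example given. The search over time is described as follows: "This will be done across all time points to find the earliest time that offers predictive value". The next sentence leaves the eventual method to be settled in the light of what the pilot shows.

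For the one cited flatus study, the section reports that the relation was "best characterized by the root mean square (RMS) deviation of the residuals from a linear fit, in units of hours", and "The optimal time for this analysis was found to be at 36 hours after surgery". Section 2.1.2 says that its linear fit "predicted first flatus as much as 5 days" ahead, with a precision of ±22 h. Section 3.2 states the intended value: "Having such information in advance of clinical measures could facilitate timely interventions".

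Patches stay on until they are removed before discharge (6.1.2). Patients leave the analysis only for necessary missing data (6.4.5), or are withdrawn for device wear that makes the data uninterpretable (6.3.7). Neither rule depends on whether flatus has occurred. Sections 6.4.3.2 and 6.4.4 add no such condition.

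**The concern.** A prediction made at time t is about an event still to come. For a patient who passed flatus before t, nothing is left to predict, yet as written that patient's cumulative activity up to t, including the part recorded after flatus, enters the correlation with time to flatus. If activity rises at or after flatus, patients with early flatus accumulate more of it by t. An inverse correlation then appears even when the signal before flatus carries no information.

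What is at stake is the meaning of the earliest predictive time. A time could be reported as predictive when part of the cohort has already recovered, whereas the device's stated value lies in information that precedes the clinical marker. Section 7.12 says that the collected information does not go back to the treating team, so the harm would be to the study's conclusion and not to participants' care.

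**Working it through.** **Plan figures.** The plan gives no figure on this point to reproduce. The inputs taken from it are n = 200 (5.3.1, 6.4.2), the 36 h reference time and the residual-RMS yardstick (6.4.3.1), and ±22 h (2.1.2).

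**Assumptions, none from the documents.** Flatus times are lognormal with median m = 30, 40, 48 or 60 h and log-SD 0.5. Each patient's activity level is lognormal with log-SD 0.4 and independent of flatus time, so there is no true prediction. After flatus, activity rises either as an abrupt step or linearly over 24 h. The yardstick is Pearson p < 0.05, which the plan does not name.

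**Step 1: share already past flatus.** F(t) = Φ(ln(t/m)/0.5). This needs no assumption about the signal.
- 24 h, m = 30: Φ(ln 0.8/0.5) = Φ(−0.446) = 33%. With m = 60: Φ(ln 0.4/0.5) = Φ(−1.833) = 3%.
- 36 h, m = 30: Φ(ln 1.2/0.5) = Φ(0.365) = 64%. With m = 60: Φ(ln 0.6/0.5) = Φ(−1.022) = 15%.

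**Step 2: nominal significance without true prediction.** The metric is cumulative activity to t against time to flatus in all 200 patients, with 4,000 simulated trials per cell. Repeat runs agree to within a few percentage points.

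| Time and rise after flatus | m = 30 | 40 | 48 | 60 h |
|---|---|---|---|---|
| 36 h, no rise | 5% | 5% | 5% | 5% |
| 36 h, 1.25-fold gradual | 9% | 5% | 5% | 5% |
| 36 h, 1.5-fold gradual | 20% | 10% | 6% | 6% |
| 36 h, 2-fold gradual | 59% | 22% | 12% | 6% |
| 36 h, 1.5-fold step | 77% | 43% | 24% | 10% |
| 36 h, 2-fold step | 100% | 91% | 65% | 25% |
| 24 h, 2-fold gradual | 9% | 6% | 5% | 4–6% |
| 24 h, 2-fold step | 76% | 24% | 11% | 6% |

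With flatus-free patients only, and activity related to remaining time, the rate is 4–6% throughout.

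**Step 3: the flatus study's own yardstick.** The relative drop in residual RMS from a linear fit is 1 − √(1 − r²). In the worst cell (36 h, 2-fold step, m = 30) the mean correlation is about −0.31, so the drop is about 1 − √(1 − 0.31²) = 4.9%; averaged over trials it is 5.2%. The SD of flatus time there is 30 × e^0.125 × √(e^0.25 − 1) = 18.1 h, so the spurious gain is 0.052 × 18.1 = 0.94 h. For the gradual 2-fold rise it is 1.4%, or 0.014 × 18.1 = 0.25 h. With no rise, chance alone gives 0.2–0.3%.

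**Step 4: what the restriction costs in precision.** The number at risk at 36 h is 200 × (1 − 0.642) ≈ 72 to 200 × (1 − 0.1535) ≈ 169. The 95% half-width for a correlation near zero is tanh(1.96/√(n − 3)): 0.23 for n = 72, 0.15 for n = 169 and 0.14 for n = 200.

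These figures are for the cumulative metric. For the instantaneous metric the result depends strongly on within-patient noise, so the two metrics are not ranked.

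**The case against.** The strongest reply is that this is a single-arm feasibility study whose plan fixes no test, threshold or risk set and leaves the final method open. On that reading the plan is silent, and the restriction can still be added. This stands, and it limits the point to an omission. It also makes the omission easy to repair now, since nothing in the current text ensures that it will be repaired.

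A second reply is that the effect is small on the one yardstick the documents tie to flatus: under one hour in the worst assumed cell, against a reported precision of ±22 h. This also stands. The high percentages in the table come from a significance rule that the plan does not contain.

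Third, the mechanism is assumed. No section says that activity rises only at or after flatus. Section 2.2 speaks of "progressive return of colonic electrical activity related to resolution of postoperative ileus and clinical recovery following surgery", which fits a gradual return and could equally reflect a rise before flatus, which would be genuine prediction. Section 2.1.2 reports stronger early activity in patients with early flatus, which leans the same way.

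Fourth, looking for the earliest time pulls towards times when few patients have passed flatus. That protects in part: at 24 h a gradual doubling stays near nominal, but an abrupt one need not.

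A reader might also infer that 36 h is supported by both cited studies. The second concerned stomach activity and first full meal, so only one bears on flatus.

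**Conclusion.** The omission is a matter of text: no section confines a time point to flatus-free patients, so a claim of prediction can rest partly on signal recorded after the event. Its size is not known. Under the stated assumptions, a 2-fold rise after flatus with no true prediction gives nominal significance in about 6–59% (gradual) or 25–100% (step) of trials at 36 h, and about 4–9% or 6–76% at 24 h. Small gradual rises barely matter, and the effect on residual RMS is slight.

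A reader might infer that the study will produce a false predictive finding, or that the correlation in the cited flatus study is an artefact. The documents support neither: they give no flatus distribution and no signal profile after flatus, and they leave the final method open. The hypothesis in 4.1, which is about correlation only, can be tested in the whole cohort as planned. This is a cheap improvement of minor to moderate importance.

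**What to change.** In 6.4.3.1, keep the whole-cohort correlation and label it as association. Add that any claim of predictive value for first flatus, and the choice of earliest time, will rest on patients who are flatus-free and still monitored at time t. Activity recorded up to t should be related to the remaining time to flatus, with the number at risk and a confidence interval reported at each t. The times and the model remain the sponsor's choice; residual RMS in hours can be kept.

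The analysis needs the clock time of flatus. Section 7.5 already requires it in the app, whereas the Appendix 3 form has only a date, so the app time should be used.

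The cost is a few sentences and a little programming, with no new visits or data. The downside is lower precision at later times: about 134–193 of 200 patients remain at 24 h and 72–169 at 36 h under the assumptions. If a true log-scale correlation of −0.3 existed, simulated power among flatus-free patients would be 59–96% at 24 h and 23–85% at 36 h, against 97–99% for the whole-cohort association. That loss falls only on predictive claims, since the association analysis keeps all patients.
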